6. PROCEDURES

6.1 Study Timetable

January 2017 – March 2017

Research & Development and ethical approval.

April 2017 – March 2022

Participant recruitment and sample collection. Laboratory analysis of samples, write up and dissemination of results.

6.2 Recruitment and Informed Consent Procedures

A member of the research team will identify and approach patients when they attend for a lower gastrointestinal endoscopy. All patients attending for colonoscopy within the specified age range are potentially eligible for this study. If the patient is in agreement, a member of the research team will explain the research project and provide a written information leaflet (see Participant Information Leaflet version 3.0 24/04/2017). Patients will be given adequate time to decide if they wish to participate and should they agree they will complete a written consent form (see Consent Form Version 2.0 15/02/2017).

A member of the research team will identify patients when they attend for a clinic appointment by discussion with the Consultant clinician responsible for the clinic. A member of the research team will approach patients when they attend for their clinic or pre-assessment appointment prior to planned surgery. Patients will have the research project explained to them and will be provided with a written information leaflet (see Participant Information Leaflet version 3.0 24/04/2017). Patients will be provided with adequate time to decide if they wish to participate and should they agree they would complete a written consent form (see Consent Form Version 2.0 15/02/2017).

All of the above would occur at one of the patient's routine clinical attendances and would not require any additional patient attendances.

7. STATISTICAL CONSIDERATIONS

Both univariate and multivariate data analysis techniques will be applied to the results to 1) identify VOC components with the best discriminating ability between the groups and 2) to develop a multivariate discriminant analysis model.

Mann-Whitney U test will be used to compare the measured metabolite concentrations between the study groups. A p value <0.05 will be taken as the level to indicate statistical significance.

Non-parametric (Kruskal-Wallis) ANOVA test will be used to compare the measured metabolite levels between the study groups. Statistically significant metabolites will be selected using False Discovery Rate (FDR) adjusted p value threshold such that less than 5% of discovered candidate markers are false positives (i.e. q-value <0.05).

The FDR strategy will be based on Benjamini-Hochberg procedure.

Receiver operating characteristic (ROC) curves will be used to determine the accuracy of a diagnostic test in classifying those with and without colorectal disease. The metabolite concentrations that exhibit significant differences ($q < 0.05$) between the cancer and positive controls (including adenomatous polyps) will be included as variables for the proposed diagnostic test. The linear discriminant analysis based on multivariate logistic regression will be subsequently used to derive a combination of the metabolite concentrations for sample classification. The optimum threshold for group discrimination will be calculated to achieve the highest possible classification accuracy. The predictive capacity of the model will be assessed on independent sample set, as described below.

Validation

The Breath and Urine metabolite model for the prediction of colorectal disease developed in the previous studies will be used to assign risk of disease in a prospective cohort. Investigators undertaking metabolite sampling and analysis will be blinded to the results of the endoscopy. Comparison of predicted disease risk and actual endoscopy findings will then be made, and the overall diagnostic accuracy (sensitivity, specificity, positive and negative predictive value, ROC curve analysis) for this non-invasive diagnostic investigation will be determined. Colonic air VOC profiles will be used for validation of paired breath results, and to gain further understanding of the mechanism of VOC production in humans.

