2. SUMMARY

Short Title	Colorectal cancer breath analysis (COBRA)
Methodology	Cohort Observational & Laboratory study
Research Site	St Mary's Hospital Charing Cross Hospital St Mark's Hospital St George's Hospital Homerton University Hospital Chelsea and Westminster Hospital West Middlesex Hospital Royal Marsden Hospital
Aims	Determine the diagnostic accuracy of the exhaled breath and urine test for the prediction of colorectal disease. To assess the acceptability of using breath and urine testing
Main Inclusion Criteria	Any patient who: 
 1. Patients aged 18 - 90 years 2. Patients seen in secondary care with symptoms of colorectal disease or referred for a lower gastrointestinal endoscopy as part of their routine clinical investigation programme 3. Patients able to understand and retain the information provided, thereby being able to give informed consent for inclusion in this study
Number of Participants	Target 2000
Endpoints	Primary endpoint 
 Once samples have been collected from 2000 patients.
Study Duration	April 2017 to April 2022

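### Marker selection and accuracy reporting take no account of age, so VOCs that track age may enter the new models and no reported AUC can show what the VOCs add to age

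*Combined protocol and SAP*

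**What the plan says.** Section 7 (Statistical Considerations) is the whole analysis plan. For pairs of groups, "Mann-Whitney U test will be used to compare the measured metabolite concentrations between the study groups", and "A p value <0.05 will be taken as the level to indicate statistical significance". For several groups, "Non-parametric (Kruskal-Wallis) ANOVA test will be used to compare the measured metabolite levels between the study groups". Multiplicity is handled at q<0.05: "The FDR strategy will be based on Benjamini-Hochberg procedure". Neither test takes covariates.

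Entry into the model is narrower than a comparison of cancer with everyone else. Metabolites that differ at q<0.05 "between the cancer and positive controls (including adenomatous polyps) will be included as variables for the proposed diagnostic test". Logistic regression is then used to "derive a combination of the metabolite concentrations for sample classification", and age is not named as a term.

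The Validation part of Section 7 applies a model from previous studies to a prospective cohort and reports sensitivity, specificity, predictive values and ROC analysis. It names no comparator based on age.

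On age itself, Section 2 admits "Patients aged 18 - 90 years", and Sections 5.1 and 5.2 make age an entry condition. Section 6.2 treats every colonoscopy attender in the age range as potentially eligible. No section matches, stratifies, restricts or adjusts for age.

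**The concern.** An age difference between cancer patients and controls is plausible on the protocol's own account. Section 3.1 expects an ageing population to raise case numbers even at constant incidence rates, and Section 3.2 says that referral guidance may miss younger patients in particular. If such a gap exists, a VOC whose level changes with age will differ between the groups even if it has no relation to cancer at a given age.

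The safeguards in the plan do not address this. False discovery control limits chance findings, whereas a VOC that differs through age is a real group difference. Blinding does not touch it. An independent sample does not remove it either, because the same link between age and cancer is present there.

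What is at stake is the use proposed in Section 3.2, triage by a GP. The GP already knows the patient's age, so the useful quantity is what the test adds to it. The plan never estimates that.

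**Working it through.** **The plan's own figure.** There is none to reproduce. Section 2 gives a target of 2000 with no number of cancers, number of positive controls, age gap or VOC-age correlation. Every numerical input below is therefore an assumption, and the results are ranges.

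**Step 1: what age alone could achieve.** For normally distributed age with a standardised gap d between groups, AUC = Φ(d/√2).

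- d = 0.5: Φ(0.354) = 0.64
- d = 0.8: Φ(0.566) = 0.71

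**Step 2: how often a VOC related only to age looks significant.** The comparison follows the plan's entry rule, cancer against positive controls, with n₁ = 100 and n₀ = 300 assumed. The VOC has within-group correlation r with age and no cancer effect given age. For the Mann-Whitney test the approximate non-centrality is d·r·√(3/π)/√(1/n₁+1/n₀), where √(3/π) = 0.977 and √(1/100+1/300) = 0.1155. The rejection rate is Φ(δ−z)+Φ(−δ−z), with z = 1.960 for p<0.05 and 2.807 for p<0.005 (two-sided).

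| d | r | δ | p<0.05 | p<0.005 |
|---|---|---|---|---|
| 0.3 | 0.2 | 0.51 | 8% | 1% |
| 0.3 | 0.3 | 0.76 | 12% | 2% |
| 0.8 | 0.2 | 1.35 | 27% | 7% |
| 0.8 | 0.3 | 2.03 | 53% | 22% |

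The nominal rates are 5% and 0.5%. The actual entry rule is q<0.05, whose effective p threshold depends on how many VOCs are tested. Selection rates would generally be lower than those in the p<0.05 column.

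**Step 3: does adjustment remove the excess?** Simulations assumed 2000 patients, of whom 60, 100 or 200 had cancer, with an age SD of 13 years, gaps of 5 and 10 years, and r from 0.1 to 0.5. Controls here were all other patients. The unadjusted Mann-Whitney test called an age-only VOC significant in 5.5% to 99.8% of runs; a linear model with age as covariate did so in 3.3% to 6.0%. With weak links the harm is small: at a 5-year gap and r = 0.1 the unadjusted rate was 5.5% to 8.3%. With no age gap both tests stayed near 5%.

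**Step 4: the q<0.05 filter and the resulting model.** One simulation used 100 VOCs, 20 tracking age and none linked to cancer, with 1000 patients (100 cancers) in each of a development and a fresh sample. At a 10-year gap and r = 0.3, the filter selected 4.1 VOCs on average, against 0.07 after age adjustment. Where any were selected, the VOC model had a mean AUC of 0.61 in the fresh sample, and adding the VOCs to age changed the AUC by −0.02. Age alone had AUC 0.71. At a 5-year gap and r = 0.2, only 0.17 VOCs were selected, against 0.13 with adjustment, so there was almost nothing to correct.

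**The case against.** Four objections have force.

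- **The entry comparison may be less exposed.** Positive controls, who include adenoma patients, may be closer in age to the cancer patients than the rest of the cohort. This stands: at a 0.3 SD gap the p<0.05 rate is only 8–12%. The documents do not show which gap applies.
- **The validated model was built elsewhere.** How its markers were chosen is not in these documents, and changing selection here would not alter its accuracy. This also stands. The selection problem concerns the refined model and the adenoma model (Section 4.1, secondary aims i and iv). Only the missing age comparator bears on the validated model.
- **Diagnostic accuracy is a legitimate target in itself.** Sensitivity, specificity and AUC in a representative sample are valid whatever makes a VOC discriminate, so age-adjusted selection is not obligatory for a prediction model. This is why adjusted selection is asked for at least as a sensitivity analysis. It does not answer the need to show the gain over age.
- **Availability of covariates.** That age is known is inferred from eligibility; no data-collection list names it. Sex is not mentioned as recorded.

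A reader might infer that any VOC correlated with age will pass the filter. The calculations do not support that: in Step 4 about 4 VOCs were selected although 20 tracked age. Nor do the documents show that the existing model is an age detector, or that it would do worst in younger patients.

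**Conclusion.** The concern holds as a gap in the plan, not as a demonstrated bias. Section 7 adjusts for multiplicity but for no covariate, and nothing elsewhere compensates. VOCs that track age may therefore enter the new models, and no AUC reported under the plan can separate VOC information from age. The size cannot be fixed from the documents. It runs from negligible, with a small age gap or weak correlation, to substantial with a gap of about 0.8 SD, where age alone would reach an AUC of about 0.71. These figures rest on assumed group sizes, age gaps, correlations and normal distributions. The missing comparison with age does not depend on them and applies to every VOC model reported.

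**What to change.** In Section 7, for the validated model and for any new model, report with confidence intervals the AUC of age alone (with sex, if recorded), of the VOC model alone, and of both together, with the increment.

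Repeat marker selection with age (and sex, if recorded) as covariates: regress rank- or log-transformed concentration on group and covariates, and apply Benjamini-Hochberg to the adjusted p values. Do this at least as a sensitivity analysis, and state which selected VOCs survive.

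Consider adjusting also for fasting duration and recruitment setting. Section 5.3 describes different fasting arrangements for endoscopy and clinic patients, and has fasting time noted for the latter.

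The cost is analysis wording and a little programming. The accuracy attributable to VOCs may look smaller.

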3. INTRODUCTION

3.1 Background

Colorectal cancer (CRC) is the 2nd commonest cause of cancer death in the UK. Survival rates are among the lowest in Europe (1) and 26% of patients present as an emergency, frequently having visited their GP before diagnosis (2-4). If diagnosed early, CRC survival rates exceed 90% (5). Whilst, reducing delay in diagnosis is therefore considered key to improving outcomes [6], initiatives to reduce delay have thus far been largely unsuccessful (6, 7). In order to improve the diagnosis of CRC, efforts should be made to determine how the risk of CRC can be assessed using sensitive primary care tests that are: valid; easy to perform, and; well tolerated by patients.

CRC screening programmes rely on detection of early-stage cancer using the faecal occult blood test (FOBT) with colonoscopy in those patients with a positive test. Trials have shown that this screening method reduced CRC mortality but not incidence rates. Even if UK CRC incidence rates remain constant, as they have for the past 30 years, with an aging population the number of cases and treatment cost are set to double in the next 50 years. The Bowel Scope programme is also being rolled out across the UK currently, aiming to perform flexible sigmoidoscopy on every person at the age of 55. Invasive screening reduces mortality but is not without risk to patients and pressurises an already overburdened healthcare service.

Risk of CRC in symptomatic patients can be assessed by different methods:

- (I) *Flexible sigmoidoscopy and colonoscopy*: The NHS currently has insufficient trained endoscopists to perform the number of procedures that would be required if flexible sigmoidoscopy were used as a first-line test for symptoms with predictive values below 3%.
- (II) *Guaiac FOBT* has good sensitivity (87-98% in CRC detection), but highly variable and often unsatisfactory specificity (13-79%), requiring the repetition of the test on multiple stool samples. To date, the FOBT is neither recommended nor available for use as an intermediate test (8-11).

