- (III) *Faecal immunochemical testing (FIT)* requires sampling only a single stool. It has been extensively tested; and is now used by many CRC screening programmes with very low prevalence rates of CRC (12). Four FIT systems are fully automated, and provide a quantitative measure of haemoglobin, allowing selection of a threshold of positivity to fit specific circumstances. As a result the research data available on sensitivity and specificity for CRC is based on small numbers of cancers. The few studies that have included adequate numbers of cancers have used older qualitative tests with a fixed threshold for positivity and were not automated. Nevertheless, the data suggest that, depending on the selected threshold for positivity, sensitivity for CRC varies between 35% and 86% with specificity between 85% and 95% (8, 9). However, there are no data on the sensitivity of the newer quantitative test for early-stage cancers.
- (IV) *Multi-target stool DNA testing*: When compared with the FIT, in a large multicentre study, the test showed better specificity (92 vs. 73%), but lower sensitivity (90 vs. 96%) (13).

At Imperial College London, we have developed a breath test for the detection of oesophagogastric adenocarcinoma from biomarker discovery to clinical trials. The assessment of volatile organic compound (VOCs) within exhaled by selected ion flow tube mass spectrometry (SIFT-MS) (14) was followed by the construction and validation of a diagnostic model using a panel of 9 VOCs in 225 patients with an area under the ROC curve (\pm SE) of 0.92 ± 0.01 and 0.87 ± 0.03 for the model and validation subsets respectively (15). We also performed cross-platform chemical validation using GC-MS. A NIHR-funded multicentre blind validation study on 396 patients (16) showed a sensitivity of 86% and specificity of

80%. In parallel with this work we have also investigated the exhalation kinetics and molecular drivers of VOCs in oesophagogastric adenocarcinoma (17-19).

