Due to the complex composition of human breath a number of sophisticated mass spectrometer based technologies have been employed for the detection of exhaled VOCs including Gas Chromatography coupled with Mass Spectrometry (GC/MS), Proton Transfer Reaction-Mass Spectrometry (PTR-MS), Selected Ion Flow Tube-Mass Spectrometry (SIFT-MS) and Ion Mobility Spectrometry (IMS). These instrumental methods all have their strengths and limitations for applications in breath analysis. We intend to use multiple analytical platforms in our proposed work as these techniques are complementary and will allow us to acquire more robust findings.

Thermal-desorption (TD) coupled to Gas Chromatography Mass Spectrometry (GC/MS) is a widely adopted method for measuring breath VOCs. Although this method requires the pre-concentration of breath volatiles prior to analysis, it allows for the comprehensive identification and semi-quantification of VOCs in unknown complex mixtures such as breath. It can separate and detect hundreds of compounds from a breath sample, allowing for VOC profiling and has therefore been used in the study of disease biomarkers for lung cancer (34, 37), breast cancer (33), colorectal cancer (32) and liver diseases (38, 39).

Selective Ion Flow Tube Mass Spectrometry (SIFT-MS) permits online, real-time VOC

quantification (40). SIFT-MS has been utilised in the study of VOCs in breath and urine from patients with conditions including cystic fibrosis and bladder cancer (41, 42). The SIFT-MS technique allows real-time detection and quantification of VOCs within biological samples such as exhaled breath without any sample preparation minimising diagnostic delay.

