5.3 Study Design and Plan

Patients recruited from the endoscopy unit will have been referred by their responsible clinician to undergo a lower gastrointestinal endoscopy (which involves a telescope test to visualise the colon). Others may be attending for colonoscopy as part of the bowel cancer screening programme or as part of routine surveillance. When patients attend the endoscopy unit, a member of the research team will discuss the research project with the patient, explain that the study involves sampling of their breath and urine while they are waiting for their endoscopy. Patients may also be asked to consent to the use of the colonic air collected during colonoscopy for analysis. Patients will then be provided with a patient

information leaflet, (see Participant Information Leaflet version 3.0 24/04/2017). Should the patient agree to participate they will be asked to sign a written consent form (see Consent Form Version 2.0 15/02/2017).

Patients recruited from secondary care will be approached either before or after a routine appointment that they will be attending as part of their clinical care. This could include general colorectal clinics, pre-operative colorectal clinics, oncology clinics, theatres or on hospital wards.

The project will be explained to them and they will be provided with an information leaflet. If they agree to participate they will be asked to sign a written consent form in order to provide breath and urine samples for the research project. Consent for colonic air sampling is not applicable to the majority of secondary care patients, only to those having a colonoscopy. No additional invasive procedures will be undertaken for the purposes of this study. A subset of patients with known cancer who are due to have a cancer resection may be asked to provide additional breath and urine samples 6–8 weeks following surgical resection of their tumour and/or if their disease should recur.

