Thermal desorption coupled to GC/MS is one of the most widely used techniques for breath biomarker discovery work for a number of reasons. Firstly, VOCs in exhaled breath are present at very low concentrations of parts-per-million (ppm) to parts-per-trillion (ppt) and pre-concentration is often necessary to allow for detection. This can be achieved by adsorption onto sorbent beds (tubes packed with tenax, carbon molecular sieve, or graphitized carbon) followed by release through thermal desorption. The coupling of a thermal desorber to a GC/MS system allows for the trapped VOCs to be released and rapidly injected on to the GC column for analysis. GC/MS is a very well established analytical technique that allows for the successful separation, identification, and semi-quantification of trace VOCs in unknown complex mixtures such as breath. This technique has allowed for the identification of over 800 compounds in breath (44). Although this technique does not allow for real-time analysis it provides a much more comprehensive analysis of the VOC profile. It will complement results obtained with SIFT-MS and can allow for cross-platform validation.

Proton-Transfer-Reaction Time-of-Flight Mass Spectrometry (PTR-ToF-MS)

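### Every VOC with q<0.05 enters the discriminant/logistic model with no stated limit, penalty or internal validation, so the refined model will overfit if tens of VOCs pass

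*Combined protocol and SAP*

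**What the plan says.** Section 7 (Statistical Considerations) builds the new diagnostic model in three steps.

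- **Screening.** Metabolites are tested one at a time and selected by the Benjamini-Hochberg procedure so that "less than 5% of discovered candidate markers are false positives (i.e. q-value <0.05".
- **Entry.** Those that differ at q<0.05 between cancers and positive controls (a group that includes adenomatous polyps) "will be included as variables for the proposed diagnostic test".
- **Combination.** "The linear discriminant analysis based on multivariate logistic regression will be subsequently used to derive a combination of the metabolite concentrations for sample classification". A cut-off is then chosen to maximise classification accuracy.

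No cap on the number of variables is given, and no events-per-variable rule, penalty, shrinkage, treatment of collinearity, cross-validation or bootstrap. Section 7 promises that the model's predictive capacity will be assessed on independent samples and points to the Validation paragraph. That paragraph applies the model from the previous studies.

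On the number of candidates, section 3.1 says of GC-MS: "It can separate and detect hundreds of compounds from a breath sample". Section 12 adds: "This technique has allowed for the identification of over 800 compounds in breath". The Summary sets a target of 2000 participants without an expected number of cancers or any split into derivation and validation sets.

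**The concern.** Controlling the false discovery rate bounds the expected proportion of false markers on the list. It does not bound the length of the list: the more VOCs truly differ, and the more correlated they are, the more enter the model. If the number of predictors becomes large relative to the number of cancers, a maximum-likelihood fit is unstable and its predicted risks are too extreme. When a linear combination of the predictors splits the two groups perfectly, no finite estimate exists.

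What is at stake is the model meant to serve secondary aim (i) in section 4.1, refinement of the current model with additional biomarkers. The cut-off would also be tuned on the overfitted scores. Testing on independent samples would show the loss, but the model carried forward would still be worse than the data allow.

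**Working it through.** The plan has no figure to reproduce: the 2000 comes with no power, precision or event calculation. The check asks what the entry rule implies over a range of assumptions.

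**Inputs**
- From the documents: n = 2000; q<0.05; hundreds of compounds per sample (300 and 800 used below); and one reference panel size, for the group's oesophagogastric model, a "panel of 9 VOCs in 225 patients".
- Assumed: 60, 100, 200 or 300 cancers (3%, 5%, 10%, 15% of 2000). The documents give no planning value.

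**1. Events per variable (EPV) = cancers / VOCs entered**

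| Cancers | 9 VOCs | 20 | 50 | 100 |
|---|---|---|---|---|
| 60 | 6.7 | 3.0 | 1.2 | 0.6 |
| 100 | 11.1 | 5.0 | 2.0 | 1.0 |
| 200 | 22.2 | 10.0 | 4.0 | 2.0 |
| 300 | 33.3 | 15.0 | 6.0 | 3.0 |

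**2. Largest model with expected shrinkage S of at least 0.9**

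p = n(S − 1) ln(1 − R²/S), where R² (Cox-Snell) is taken as 15% to 50% of its maximum, 1 − exp{2[φ ln φ + (1 − φ) ln(1 − φ)]}, and φ = cancers/2000.

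For 60 cancers, φ = 0.03 and the maximum is 0.236. At 15% of it, R² = 0.0354 and p = 2000 × (−0.1) × ln(1 − 0.0354/0.9) = 8.0. At 50%, p = 28.1. The same formula gives 11 to 40 VOCs for 100 cancers and 17 to 62 for 200. For 300 (φ = 0.15, maximum 0.571) it gives 20 to 76. The plan sets no such limit.

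**3. Simulation of the rule as written**

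Mann-Whitney test on each VOC, Benjamini-Hochberg at 5%, all selected VOCs into a plain logistic fit, then tested on fresh data. Assumptions: 300 or 800 VOCs in blocks of 10 with correlation 0.5; 30 to 150 true VOCs shifted by 0.4 SD; n = 2000; 8 runs per cell. Ranges are across cells.

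| Cancers | VOCs selected | EPV | Apparent AUC | Fresh-data AUC | Calibration slope |
|---|---|---|---|---|---|
| 60 | 17–85 | 3.6–0.7 | 0.78–0.98 | 0.70–0.86 | 0.33–0.68 |
| 100 | 30–137 | 3.4–0.7 | 0.80–0.98 | 0.70–0.86 | 0.28–0.64 |
| 200 | 32–157 | 6.3–1.3 | 0.77–0.96 | 0.71–0.88 | 0.48–0.76 |
| 300 | 32–157 | 9.5–1.9 | 0.77–0.96 | 0.72–0.89 | 0.56–0.83 |

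A slope of 1 means that risks are correctly spread; below 1 they are too extreme.

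**4. Plain fit against cross-validated ridge** (three further simulations, 10 to 25 runs per setting)
- *800 VOCs, 500 positive controls.* 60 cancers, 46 VOCs: AUC 0.83 v 0.85, slope 0.37 v 0.77. 100 cancers, 88 VOCs: AUC 0.84 v 0.89, slope 0.31 v 1.12. With 13 to 19 VOCs the AUC gain was at most 0.003 and the plain slope 0.72 to 0.82.
- *800 VOCs, strong signal (shifts of 0.35 to 0.45 SD in one direction).* 200 cancers, 1800 controls, 102 VOCs: AUC 0.962 v 0.973, slope 0.42 v 0.96. 100 cancers, 1900 controls, 23 VOCs: AUC 0.883 v 0.884, slope 0.81 v 1.03.
- *300 VOCs, 60 to 300 cancers.* With 28 to 62 VOCs, the plain slope was 0.17 to 0.63 and AUC 0.003 to 0.022 below ridge. With 9 to 13 VOCs, AUC was equal and the plain slope 0.84 to 0.97.

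**5. Complete separation**

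The asymptotic threshold is p* = n × min over (a, b) of E[max(aY + bYX − Z, 0)²], with Y = ±1 the outcome, X the standardised true score and Z standard normal. For a linear-predictor SD from 2.5 down to 0 and n = 2000, about 130 to 233 VOCs are needed with 60 cancers, 187 to 328 with 100, and 300 to 517 with 200. With fewer controls the threshold drops: 83 to 142 VOCs for 60 v 440, and 54 to 89 for 60 v 140.

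Simulated frequencies fit this. There were 0 of 8 runs in every n = 2000 cell of step 3, and 1 of 10 and 3 of 10 with 500 controls in step 4. In the strong-signal simulation, one cell with 100 cancers, 1900 controls and about 90 VOCs separated in 9 of 12 runs (median slope 0.04). Its signal is stronger than the threshold calculation covers.

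**The case against.** Several points against the concern stand.

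- **The cancer count is unknown.** A reader might infer 60 to 100 cancers, from 3% to 5% of 2000. The documents do not support that as likely. Section 5.3 also recruits from "general colorectal clinics, pre-operative colorectal clinics, oncology clinics, theatres or on hospital wards" and mentions patients with known cancer awaiting resection, so the count could be well above that of an endoscopy series. The range must therefore be shown.
- **The panel may be small.** The 800 compounds are what the technique has identified in breath generally, not this study's candidate list. The one panel size in the documents is 9. With 9 VOCs and 200 cancers EPV is 22, and the problem largely disappears.
- **A plain fit is not prescribed.** A reader might take section 7 to require an unpenalised model. It is silent, and the fair criticism is that nothing is specified.
- **Separation is not the likely outcome.** A reader might infer that the fit will break down. At n = 2000 that takes either well over 100 VOCs or a very strong signal. It becomes more plausible if fitting is confined to cancers and positive controls, or if a validation set is carved out of the 2000.
- **The risk of disease in the Validation paragraph is not from this model.** A reader might link the two, but the text assigns that risk with the model from the previous studies.
- **The remedy gains little discrimination.** AUC differences are small and come from few runs. Calibration slope is not a planned measure, and ridge itself reached only 0.77 in one setting. A pre-specified maximum panel size would also close the gap.

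The promised assessment on independent samples does not answer the point. It would detect optimism without preventing it, and no set is clearly reserved for the newly derived model.

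**Conclusion.** The concern holds in a conditional form. Section 7 has an open-ended entry rule with no limit, penalty or internal validation, and false discovery rate control does not supply one. For assumed counts of 60 to 300 cancers, once about 30 or more VOCs pass, EPV falls below 10, in most settings well below. A plainly fitted refined model then overfits: calibration slope is roughly 0.2 to 0.8, apart from the cell that mostly separated, and AUC is about 0.00 to 0.05 below ridge. Miscalibration is the main harm; the loss of discrimination is small. If only about 9 VOCs pass with 200 cancers, little is lost.

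These sizes rest on assumed cancer counts, effect sizes and correlations, and on 8 to 25 runs per setting. They show direction and order of magnitude. The point is an improvement to the derivation of a secondary-aim model. It does not affect the planned test of the existing model.

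**What to change.** In section 7, derive the combination by penalised logistic regression (ridge or elastic net). Choose the penalty by cross-validation and repeat the q<0.05 filter inside each fold, so that selection is part of what is validated. When the new model is assessed on the independent set, report calibration slope with AUC. Keep the q<0.05 list as the univariate result.

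The cost is a change of analysis wording and standard software; no extra patients or samples are needed. The downsides are shrunken coefficients that are slightly harder to present, and mild over-shrinkage in some settings (ridge slopes up to 1.12 in step 4). With 9 to 13 VOCs selected, ridge cost no AUC.
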